1.6. Clinical Experience

1.6.1. Clinical Efficacy With Topical INCB018424 Cream in Vitiligo

An investigator-initiated, 20-week, open-label POC study with extension up to 52 weeks of INCB018424 cream 1.5% BID is currently ongoing. The primary outcome of the study is improvement in VASI from baseline to Week 20. Eleven patients with vitiligo with a minimum of 1% affected BSA were enrolled into the study. At Week 20, 76% improvement in facial VASI score was observed in patients with significant facial vitiligo, and 26% improvement in overall VASI from baseline to Week 20 was also observed. These changes were considered to be a clinically meaningful response. Slower response was observed in acral areas as compared with facial areas. Reported AEs considered related to drug were mild and included erythema, hyperpigmentation in skin where drug was applied, and transient acne. Overall, INCB018424

cream was well-tolerated. The hyperpigmentation was observed in areas with subsequent repigmentation and may be predictive of response to study drug.

[figure not shown]
1.6.2. Clinical Efficacy With Topical INCB018424 Cream in Psoriasis

[figure not shown]
In a double-blind, vehicle- or comparator-controlled, ascending dose, safety, tolerability, PK, and preliminary efficacy study of INCB018424 cream in subjects with plaque psoriasis (Study INCB 18424-201), efficacy was demonstrated with both the 1% cream applied QD and the 1.5% cream applied BID with a trend toward a dose response. Improvement in lesion thickness, erythema, scaling, and reduction in total lesion area were observed in comparison to the vehicle. Reductions in mean lesion scores were 53% for 1% cream QD versus 32% for vehicle ($p \leq 0.05$); 54% for 1.5% cream BID versus 27% for vehicle ($p \leq 0.05$); 46% for 1.5% cream BID versus 40% for Dovonex® cream; and 58% for 1.5% cream BID versus 44% for Diprolene AF® cream.

[figure not shown]
[REDACTED]

[figure not shown]
Study INCB 18424-203 was a 12-week, randomized, multicenter, parallel-group, vehicle-controlled, double-blind, dose-ranging study designed to evaluate the safety and efficacy of QD application of INCB018424 cream (0.5%, 1.0%, or 1.5%) relative to vehicle cream in subjects with stable plaque psoriasis. Within each active treatment group, the mean scores for the individual and total psoriasis lesion assessments, the PASI, the Physician's Global Assessment, and the mean treatable percent BSA decreased from baseline to each subsequent assessment, which indicated an overall lessening of disease severity. Thus, the efficacy analyses collectively revealed that all 3 doses of INCB018424 cream, when applied topically QD for 12 weeks, were effective in decreasing the individual signs of lesion severity, lesion area, and the overall disease severity of psoriatic plaques.

[REDACTED]

1.6.5. Oral INCB018424 (Ruxolitinib) Safety

[figure not shown]
In the randomized period of the 2 pivotal studies in myelofibrosis, COMFORT-I and COMFORT-II, discontinuation because of AEs regardless of causality was observed in 11.3% of subjects. The most frequently reported adverse drug reactions were thrombocytopenia and anemia. Hematological adverse reactions (any CTCAE grade) included anemia (82.4%), thrombocytopenia (69.8%), and neutropenia (16.6%). Anemia, thrombocytopenia, and neutropenia are dose-related effects. The 3 most frequent nonhematological adverse reactions were bruising (21.6%), dizziness (15.3%), and headache (14.0%). The 3 most frequent nonhematological laboratory abnormalities were increased alanine ALT (27.2%), increased AST (18.6%), and hypercholesterolemia (16.9%).

Long-term follow-up in subjects with myelofibrosis (including 615 subjects treated with ruxolitinib during the controlled and extension phases of Studies INCB 18424-251 cutoff 01 OCT 2012; COMFORT-I: 02 SEP 2012; and COMFORT-II: 01 SEP 2012) has shown that, as expected, the numbers and proportions of AEs and SAEs has increased; however, no new safety signals have emerged (median duration of exposure for this population is 27.6 months, with 1345.78 patient-years of exposure).

In Study INCB 18424-258, in subjects with myelofibrosis with a platelet count between 50 and $100 \times 10^9/L$, beginning treatment with 5 mg BID was well-tolerated, avoided levels of thrombocytopenia associated with a high risk of significant bleeding, and provided an opportunity to increase the dose of ruxolitinib in a safe manner.

Overall, the safety profile of ruxolitinib in the PV population is generally consistent with that observed in the myelofibrosis population. Ruxolitinib was generally well-tolerated in subjects with PV, and only a small proportion of subjects discontinued ruxolitinib because of AEs (3.6%). Most of the AEs were managed by dose modifications. Hematological toxicities were less frequent and less severe in subjects with PV as compared with those observed in subjects with myelofibrosis. No new safety signals emerged from a study in pancreatic cancer in combination with capecitabine. The AE profile of ruxolitinib was also assessed in 198 healthy subjects, subjects with various degrees of renal (n = 32) or hepatic (n = 24) impairment, and subjects with RA (n = 59). Adverse events were, in general, mild and resolved without interventions.

A thorough QT study was conducted in 50 healthy subjects. There was no indication of a QT/QTc-prolonging effect of ruxolitinib in single doses up to a supratherapeutic dose of 200 mg, indicating that ruxolitinib has no effect on cardiac repolarization.

2. STUDY OBJECTIVES AND ENDPOINTS

2.1. Study Objectives

2.1.1. Primary Objective

- To establish the efficacy of 24 weeks of treatment with INCB018424 cream in subjects with vitiligo.

2.1.2. Secondary Objectives

- To estimate the dose-response relationship of INCB018424 cream at Weeks 24 and 52.
- To evaluate the safety and tolerability of INCB018424 cream in subjects with vitiligo.

2.2. Study Endpoints

2.2.1. Primary Endpoint

- Proportion of subjects treated with INCB018424 cream who achieve a $\geq 50\%$ improvement from baseline in F-VASI score (F-VASI50) at Week 24 compared with subjects treated with vehicle.

2.2.2. Secondary Endpoints

2.2.2.1. Key Secondary Endpoints

- Proportion of subjects who achieve an F-PhGVA of clear or almost clear at Week 24.
- Proportion of subjects who achieve a $\geq 50\%$ improvement from baseline in T-VASI at Week 52.

2.2.2.2. Other Secondary Endpoints

- Assessment of the dose response on percentage change from baseline in F-VASI during the treatment periods.
- Mean and percentage change from baseline in F-VASI score during the treatment periods.

- Proportion of subjects who achieve an F-VASI50 during the treatment periods.
- Percentage change from baseline in F-BSA repigmentation during the treatment periods.
- Percentage change from baseline in T-BSA repigmentation during the treatment periods.
- Mean and percentage change from baseline in T-VASI score during the treatment periods.
- Mean and percentage change from baseline in VETF during the treatment periods.
- Proportion of subjects in each F-PhGVA and T-PhGVA category during the treatment periods.
- Proportion of subjects in each F-PaGVA and T-PaGVA category during the treatment periods.
- Proportions of subjects in each PaGIC-V category during the treatment periods.
- Proportion of subjects who report PaGIC-V of very much improved or much improved during the treatment periods.
- Times to achieve an F-VASI50 and T-VASI50.
- Times to achieve an F-PhGVA and T-PhGVA of clear or almost clear.
- Time to achieve a PaGIC-V of very much improved or much improved.
- Safety and tolerability assessed by monitoring the frequency, duration, and severity of AEs, physical examination, vital signs, and laboratory data for hematology, serum chemistry, and urinalysis.

3. SUBJECT ELIGIBILITY

Deviations from eligibility criteria are not allowed because they can potentially jeopardize the scientific integrity of the study, regulatory acceptability, and/or subject safety. Therefore, adherence to the criteria as specified in the Protocol is essential.

3.1. Subject Inclusion Criteria

A subject who meets all of the following criteria may be included in the study:

1. Male and female subjects aged 18 to 75 years, inclusive.
2. Subjects with a clinical diagnosis of vitiligo.
3. Subjects with vitiligo with depigmented areas including:
 - a. at least 0.5% of the total BSA on the face (0.5% BSA is approximately equal to the area of the subject's palm [without digits]) AND
 - b. at least 3% of the total BSA on nonfacial areas (3% BSA is approximately equal to the area of 3 of the subject's handprints [palm plus 5 digits]).
4. Subjects who agree to discontinue all agents used to treat vitiligo from screening through the final follow-up visit. Over-the-counter preparations deemed acceptable by the investigator and camouflage makeups are permitted.
5. If receiving concomitant medications for any reason, must be on a stable regimen and anticipate staying on a stable regimen.
6. Willingness to avoid pregnancy or fathering of children based on the following criteria:
 - a. Woman of nonchildbearing potential (surgically sterile with a hysterectomy and/or bilateral oophorectomy OR postmenopausal, defined by last menstrual period > 12 months before screening and confirmed by FSH).
 - b. Woman of childbearing potential who has a negative serum pregnancy test at screening and a negative urine pregnancy test before the first dose on Day 1 and who agrees to take appropriate precautions to avoid pregnancy from screening through safety follow-up. Permitted methods that are highly efficacious in preventing pregnancy (see [Appendix A](#)) should be communicated to the subject and their understanding confirmed.
 - c. Man who agrees to take appropriate precautions to avoid fathering children from screening through safety follow-up. Permitted methods that are highly efficacious in preventing pregnancy (see [Appendix A](#)) should be communicated to the subject and their understanding confirmed.
7. Ability to comprehend and willingness to sign an ICF.

3.2. Subject Exclusion Criteria

A subject who meets any of the following criteria will be excluded from the study:

1. Conditions at baseline that would interfere with evaluation of vitiligo.
2. Subjects who are receiving any kind of phototherapy, including tanning beds.
3. Subjects with other dermatologic disease besides vitiligo whose presence or treatments could complicate the assessment of repigmentation.
4. Subjects who have used skin bleaching treatments for past treatment of vitiligo or other pigmented areas.
5. Subjects who have received any of the following treatments within the minimum specified timeframes.
 - a. Use of any biologic, investigational, or experimental therapy or procedure for vitiligo within 12 weeks or 5 half-lives (whichever is longer) of screening. Investigational biologics should be discussed with the sponsor to determine if a longer period of discontinuation is required.
 - b. Use of laser or light-based vitiligo treatments, including tanning beds, within 8 weeks of screening.
 - c. Use of immunomodulating oral or systemic medications (eg, corticosteroids, methotrexate, cyclosporine) or topical treatments that may affect vitiligo (eg, corticosteroids, tacrolimus/pimecrolimus, retinoids) within 4 weeks of screening.
6. Use of any prior and concomitant therapy not listed above that may interfere with the objective of the study as per discretion of the investigator, including drugs that cause photosensitivity or skin pigmentation (eg, antibiotics such as tetracyclines, antifungals) within 8 weeks of screening.
7. Subjects with a clinically significant abnormal TSH or free T4 at screening as determined by the investigator.
8. Subjects with cytopenias at screening, defined as follows:
 - a. Leukocytes $< 3 \times 10^9/L$ ($2.5 \times 10^9/L$ for subjects who are African-American).
 - b. Neutrophils $<$ lower limit of normal.
 - c. Lymphocytes $< 0.8 \times 10^9/L$.
 - d. Hemoglobin $< 10 \text{ g/dL}$.
 - e. Platelets $< 100 \times 10^9/L$.
9. Subjects with severely impaired liver function (Child-Pugh Class C) or ALT or AST $\geq 1.5 \times \text{ULN}$ on repeated assessment.
10. Subjects with impaired renal function with estimated creatinine clearance less than 60 mL/min.
11. Positive serology test results for HIV, for hepatitis B surface antigen or core antibody, or for hepatitis C virus antibody with detectable RNA at screening.

12. Subjects taking potent systemic CYP3A4 inhibitors or fluconazole within 2 weeks or 5 half-lives, whichever is longer, before the baseline visit (topical agents with limited systemic availability are permitted, see [Appendix B](#)).
13. Subjects who have previously received JAK inhibitor therapy, systemic or topical (eg, ruxolitinib, tofacitinib, baricitinib, filgotinib, lestaurtinib, pacritinib).
14. Women who were pregnant during the 12 months before screening.
15. Women who are breastfeeding.
16. Current or recent history (< 30 days before screening and/or < 45 days before randomization) of a clinically meaningful bacterial, fungal, parasitic, or mycobacterial infection.
17. History of unstable ischemic heart disease (including percutaneous cardiac intervention, myocardial infarction, or anginal acceleration within the past 6 months) or uncontrolled hypertension (blood pressure > 150/90 mmHg on at least 2 subsequent readings).
18. History of alcoholism or drug addiction within 1 year before screening, or current alcohol or drug use that, in the opinion of the investigator, will interfere with the subject's ability to comply with the administration schedule and study assessments.
19. Current treatment or treatment within 30 days or 5 half-lives (whichever is longer) before the baseline visit with another investigational medication or current enrollment in another investigational drug protocol.
20. Use of any prohibited medications (see Section [5.6.3](#)) within 14 days or 5 half-lives (whichever is longer) of the baseline visit.
21. Donation of blood within 6 weeks before screening or of plasma within 2 weeks before screening and unwillingness to forego further blood product donation during the study.
22. Receipt of blood products within 2 months before screening.
23. Subjects with a history of malignancy, except for the following adequately treated, nonmetastatic malignancies: basal cell skin cancer not involving areas with vitiligo, squamous cell carcinomas of the skin not involving areas with vitiligo, or *in situ* cervical cancer.
24. Subjects who anticipate receiving a live or live-attenuated vaccination from screening through the final follow-up visit.
25. Subjects with known allergy or reaction to any component of the study formulation.
26. Subjects who, in the opinion of the investigator, are unable or unlikely to comply with the administration schedule and study evaluations.

4. INVESTIGATIONAL PLAN

4.1. Overall Study Design

This is a 3-part, randomized, double-blind, and vehicle-controlled study in subjects with vitiligo who have depigmented areas including at least 0.5% of the total BSA on the face and at least 3% of the total BSA on nonfacial areas as determined by the palmar or handprint (palm plus 5 digits) method. Approximately 150 subjects, aged 18 to 75 years, will be randomized to 1 of 4 dose strengths of INCB018424 cream (1.5% BID, 1.5% QD, 0.5% QD, 0.15% QD) or vehicle in a 1:1:1:1 ratio and stratified by age (≤ 30 or > 30 years).

Subjects will receive blinded treatment for up to 52 weeks to examine efficacy, safety, and tolerability. The 3 parts of the study include a 24-week, double-blind, vehicle-controlled treatment period; a 28-week, continued, double-blind treatment period; and a 104-week, open-label extension period (see [Figure 1](#)). The primary endpoint of F-VASI50 will be evaluated at Week 24. After completion of the Week 24 assessments, subjects randomized to vehicle will be randomized to 1 of the 3 higher active treatment groups in a 1:1:1 ratio while maintaining the blind. Subjects in the 0.15% QD dose group who do not achieve a $\geq 25\%$ improvement from baseline on F-VASI (nonresponders of F-VASI25) will be re-randomized to 1 of the 3 higher active treatment groups while maintaining the blind. Subjects randomized to INCB018424 0.15% QD who achieve a $\geq 25\%$ improvement from baseline on F-VASI will remain on the same dose until Week 52. Subjects randomized to INCB018424 1.5% BID, 1.5% QD, and 0.5% QD will remain on the same dose until Week 52.

At any time during the study, if a subject has expansion of existing areas of depigmentation or development of new areas of depigmentation, then after a visit to document the VASI score and other measures of vitiligo, subjects are to apply study drug to those areas that are new or expanded since baseline in addition to areas treated since baseline as long as the total BSA to be treated does not exceed 20%. This visit may be unscheduled.

After completion of the Week 52 assessments, subjects who continue to be eligible for the study will be offered the opportunity to receive an additional 104 weeks of open-label treatment with INCB018424 1.5% cream BID. To be eligible, subjects must have completed the baseline, Week 24, and Week 52 visit assessments, be compliant with study medication, have no clinically significant changes in laboratory parameters from baseline (must meet entry criteria regarding cytopenias and liver assessments) and, in the opinion of the investigator, have no safety concerns regarding the previous 52 weeks of treatment with INCB018424 cream. In the open-label extension, subjects may be offered low-dose narrow band-UVB phototherapy in addition to INCB018424 cream in consultation with the investigator and sponsor.

[figure not shown]
Subjects who are eligible for the open-label extension who have complete facial repigmentation (F-PhGVA score of 0) may stop applying study drug to the face, decrease the application rate to QD, or continue BID based on investigator judgement at Weeks 52 and 80 (after Week 80, subjects may also be permitted to modify their treatment regimen after the investigator has consulted with the sponsor). Subjects may continue to apply INCB018424 1.5% QD or BID to areas of vitiligo on the body; dose will be determined by the investigator based on level of repigmentation. A subject who had decreased the dose to QD or stopped applying INCB018424

to the face who has a loss of pigmentation on the face (F-PhGVA of at least 1) may increase the dose from QD to BID or restart application of INCB018424 1.5% BID after a visit to document the F-VASI score and other measures of vitiligo.

Sites will remain blinded to study drug, but some personnel at Incyte without direct contact with sites will be unblinded for the interim analyses. This internal committee will be charged with evaluating the unblinded interim analysis results (when at least 50% subjects first have Week 12 and then Week 24 data available). As full repigmentation is anticipated to be a slow process, the interim analysis results will determine preliminary efficacy of the treatment groups for future study and planning. After Week 24, the members of the primary endpoint assessment team from Incyte will be unblinded.

If any other skin products that are permitted under the study Protocol are used, subjects should continue these unchanged during the study.

Figure 1: Study Design Schema

* Rerandomization to 0.5% QD, 1.5% QD, or 1.5% BID at Week 24 for vehicle group.

† Rerandomization to 0.5% QD, 1.5% QD, or 1.5% BID if <25% improvement in F-VASI at Week 24.

BID = twice daily; F-VASI = facial Vitiligo Area Scoring Index; QD = once daily.

4.2. Measures Taken To Avoid Bias

This is a randomized, placebo-controlled study with a 52-week double-blind period. Subjects will be randomized to 1 of 5 dose groups at baseline. After completion of the Week 24 assessments, subjects randomized to vehicle will be randomized to 1 of the 3 higher active treatment groups while maintaining the blind. Subjects in the 0.15% QD dose group who do not achieve a $\geq 25\%$ improvement from baseline on F-VASI (nonresponders of F VASI25) will be re-randomized to 1 of the 3 higher active treatment groups while maintaining the blind. Subjects randomized to INCB018424 0.15% QD who achieve a $\geq 25\%$ improvement from baseline on F-VASI will remain on the same dose until Week 52. Subjects randomized to INCB018424 1.5% BID, 1.5% QD, and 0.5% QD will remain on the same dose until Week 52.

4.3. Number of Subjects

The study will enroll approximately 150 subjects randomized equally to 1 of 5 treatment groups.

4.4. Duration of Treatment and Subject Participation

Screening is up to 28 days (4 weeks), the double-blind, vehicle-controlled, treatment period is 24 weeks, the continued double-blind treatment period is 28 weeks (52 weeks cumulative double-blind), the optional open-label extension treatment is 104 weeks, and safety follow-up is 24 weeks. Total duration is up to 184 weeks.

4.5. Overall Study Duration

The study begins when the first subject signs the ICF. The end of the study will occur when all subjects have discontinued study drug and have completed applicable follow-up assessments.

4.6. Study Termination

The investigator retains the right to terminate study participation at any time, according to the terms specified in the study contract. The investigator is to notify the IRB/IEC in writing of the study's completion or early termination, send a copy of the notification to the sponsor or sponsor's designee, and retain 1 copy for the site study regulatory file.

The sponsor may terminate the study electively or if required by regulatory decision. If the study is terminated prematurely, then the sponsor will notify the investigators, the IRBs and IECs, and regulatory bodies of the decision and reason for termination of the study.

5. TREATMENT

5.1. Treatment Assignment

5.1.1. Subject Numbering and Treatment Assignment

The study will use an IRT for management of study enrollment. The system will assign the subject study number, track subject visits, randomize according to the defined parameters, maintain the blinding, and manage of study drug inventory.

5.1.2. Randomization and Blinding

For subjects who have met all study entry criteria and none of the exclusion criteria, the IRT should be contacted at baseline to obtain the study drug assignment. The system will assign the subject study number, track subject visits, randomize according to the defined parameters, and maintain the blind. The system will employ a configurable stratification algorithm with limits set to subject age (≤ 30 and > 30 years). Subjects will be randomized to 1 of 4 dose strengths of INCB018424 cream (1.5% BID, 1.5% QD, 0.5% QD, 0.15% QD) or vehicle in a 1:1:1:1:1 ratio. If any of the limits are reached, then the IRT will stop assigning randomization numbers to that group, and no additional subjects will be enrolled in that group. Subjects, investigators, and the sponsor (with the exception of members of the interim analysis and primary endpoint analysis assessment teams) will remain blinded to each subject's treatment assignment throughout the

study. Emergency unblinding will occur if an AE requires the investigator to be made aware of the subject's treatment assignment (see emergency unblinding procedures in Section 8.4 and refer to the Study Reference Manual).

5.2. INCB018424 Cream or Matching Vehicle

5.2.1. Description and Administration

INCB018424 cream or matching vehicle will be applied as a thin film BID, with applications at least 8 hours apart. The dose strengths for INCB018424 cream are 1.5%, 0.5%, and 0.15% (w/w free base equivalent) in a cream formulation along with the matching vehicle cream formulation containing only the vehicle.

Study drug will be applied in the clinic on the day of a study visit. The application regimen is to be determined by weighing a tube before and after the subject applies a thin film of study drug to the affected areas. For the determination of dosage, subjects should remove study drug from the tube in fingertip units until all of the areas to be treated are covered by a thin film. On the day of a visit, subjects should not apply the study drug at home and will apply the morning dose of study drug from the new kit in the clinic. If a subject has vitiligo present on more than 20% of BSA, the application of study drug will be limited to \leq 20% of the subject's total BSA. Subjects will be advised to limit use to no more than 1 tube per application. Application instructions will be provided at study visits and via a diary card given to the subjects.

At each visit, an estimate of the percent BSA to be treated will be used by the IRT system to calculate the number of tubes of study drug to be dispensed. All areas identified at baseline should continue to be treated through the end of the double-blind period (Week 52) unless the subject meets criteria for stopping study drug because of an AE. If there are new areas to be treated, including expansion of existing areas or development of new areas, study drug should be applied to these areas in addition to the areas treated at baseline (up to 20% BSA), and the percentage of BSA to be treated will be recalculated and increased. This new estimate will be entered into the IRT system to calculate the number of tubes of study drug to be dispensed.

[figure not shown]

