7.6.1. Vitiligo Area and Severity Index

Areas affected by depigmentation due to vitiligo will be assessed using the VASI, which is a quantitative clinical tool that is analogous to the PASI used in psoriasis and is based on a composite estimate of the overall area of vitiligo patches at baseline and the degree of macular repigmentation within these patches over time.

In this study, F-VASI will be determined. F-VASI will be the percentage of depigmented vitiligo skin expressed as a percentage of BSA (hand unit) on the face and estimated by the investigator using the palmar or handprint (palm plus 5 digits) method. This will be an additional variable to be analyzed in addition to the vitiligo head/neck subscore.

The total body VASI is calculated using a formula that includes contributions from all body regions (possible range, 0-100).

$$VASI = \sum_{\text{all body sites}} [\text{hand units}] \times [\text{Residual Depigmentation}]$$

Briefly, the body is divided into the following 6 separate and mutually exclusive sites: head/neck, hands, upper extremities (excluding hands), trunk, lower extremities (excluding feet), and feet. The percentage of vitiligo involvement is estimated in hand units by the same investigator during the entire course of the study. Hand unit is based on subject's hand size. Investigator uses his/her hand to mimic the subject's hand size to evaluate % BSA vitiligo involvement. The degree of depigmentation for each body site was determined and estimated to

the nearest of the following percentages: 0, 10%, 25%, 50%, 75%, 90%, or 100%. At 100% depigmentation, no pigment is present; at 90%, specks of pigment are present; at 75%, the depigmented area exceeds the pigmented area; at 50%, the depigmented and pigmented area are equal; at 25%, the pigmented area exceeds the depigmented area; at 10%, only specks of depigmentation are present. The VASI is then derived by multiplying the values assessed for the vitiligo involvement by the percentage of affected skin for each body site and summing the values of all body sites together ([Hamzavi 2004](#), [Dicle 2015](#)). See [Appendix C](#) for full assessment tool.

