7.6.2. Body Surface Area

At each visit, the BSA affected with vitiligo for each of 4 regions (head/neck [H], upper limbs [UL], trunk [T], and lower limbs [LL]) as a percent of the total BSA, as well as the face separately (depigmented area as a percent of the total area of the face) will be determined to the nearest 0.1% using, as guides, the palm plus 5 digits, with fingers tucked together and thumb tucked to the side (handprint), as 1% BSA and the thumb as 0.1% BSA.

If the subject has areas that exceed 20% that will not be treated with study drug, the BSA of these areas should be noted.

If worsening of vitiligo is present, then new areas, expansion of existing areas, or both are noted as present since the prior visit.

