Briefly, the body is divided into the following 6 separate and mutually exclusive sites: head/neck, hands, upper extremities (excluding hands), trunk, lower extremities (excluding feet), and feet. The percentage of vitiligo involvement is estimated in hand units by the same investigator during the entire course of the study to eliminate variations in hand size. The degree of depigmentation for each body site was determined and estimated to the nearest of the following percentages: 0%, 10%, 25%, 50%, 75%, 90%, or 100%. At 100% depigmentation, no pigment is present; at 90%, specks of pigment are present; at 75%, the depigmented area exceeds the pigmented area; at 50%, the depigmented and pigmented area are equal; at 25%, the pigmented area exceeds the depigmented area; at 10%, only specks of depigmentation are present. The VASI is then derived by multiplying the values assessed for the vitiligo involvement by the percentage of affected skin for each body site and adding the values of all

body sites together (Hamzavi et al 2004, Dicle 2015). See Appendix C of the Protocol for the full assessment tool.

The categorical variable T-VASI50 is defined to be equal to 1 for subjects achieving an improvement in T-VASI of at least 50% and 0 for those achieving improvement in T-VASI of less than 50%. A subject is said to be a T-VASI50 responder or have achieved a T-VASI50 response if T-VASI50 = 1.

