#### 7.4.1. Efficacy Analysis for Key Secondary Endpoints

The percentage of F-PhGVA responders at Week 24, as well as the percentage of T-VASI50 responders at Week 52, will be analyzed using similar logistic regression as specified in the primary efficacy analysis. The NRI rule for missing data is the same as in F-VASI50. The graphical approach as specified in Figure 2 will be used to control the family-wise error rate.

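### Week 52 T-VASI50 counts skin that the 20% BSA cap leaves untreated, and the visible T13/T23 model has no term for baseline extent

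*Protocol*

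**What the plan says.** **Treatment cap.** Protocol 5.2.1: "If a subject has vitiligo present on more than 20% of BSA, the application of study drug will be limited to" 20% of total BSA or less. New or expanded lesions may also be treated, but only "as long as the total BSA to be treated does not exceed 20" percent (Protocol 4.1).

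**Entry.** Protocol 3.1 sets minimum extents: 0.5% of BSA on the face and "at least 3% of the total BSA on nonfacial areas". No criterion in Protocol 3.1 or 3.2 sets a maximum. The cap rule itself foresees subjects above 20%.

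**Endpoint.** Protocol 7.6.1: "The total body VASI is calculated using a formula that includes contributions from all body regions (possible range, 0-100"). Untreated skin is not excluded. SAP 7.2.1: "The categorical variable T-VASI50 is defined to be equal to 1 for subjects achieving an improvement in T-VASI of at least 50" percent.

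**Week 52 tests.** SAP 3.2.2 defines T13 (1.5% BID vs 0.5% QD) and T23 (1.5% QD vs 0.5% QD) on T-VASI50. They are tested by Bonferroni-Holm at 0.025 overall once T12 and T22 are both rejected. SAP 7.4.1 analyses F-PhGVA response "as well as the percentage of T-VASI50 responders at Week 52" with a logistic regression like that of the primary endpoint. SAP 7.3.1 gives the predictors of that model as treatment group and age stratum.

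**Data on extent.** Protocol 7.6.2: "If the subject has areas that exceed 20% that will not be treated with study drug, the BSA of these areas should be noted". SAP 6.1.2 summarizes baseline total BSA. Total BSA is not a stratification factor, a model term or a subgroup in SAP 7.6. The only sensitivity analysis listed (SAP 7.3.2) is a per-protocol analysis of the primary endpoint.

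**The concern.** The cap makes T-VASI50 a different hurdle for different subjects. At or below 20% BSA, half of the treated disease must repigment. Above 20%, the treated skin must also make up for skin that receives no drug. Extent at baseline is then strongly prognostic for the endpoint, through the trial's own rules.

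T13 and T23 are the only dose-versus-dose comparisons in the multiplicity scheme. Subjects who can hardly respond on any dose pull both arms' rates down in proportion, so the difference shrinks while the arm size stays the same. The hurdle looks high even without this: the open-label study described in Protocol 1.6.1 saw 26% overall VASI improvement at Week 20, against 76% on the face.

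**Working it through.** **1. The plan's own power figure.** Protocol 9.2 claims more than 90% power for F-VASI50 with 25 per group, two-sided alpha 0.025 and Fisher's exact test. Exact enumeration gives 95.9% for 55% vs 5% and 91.5% for 50% vs 5%, so the claim is reproduced. No power is stated for T-VASI50 at Week 52.

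**2. The hurdle as a function of extent.** T-VASI is the sum of hand units times degree of depigmentation (Protocol 7.6.1). Let B be affected BSA in percent and min(B, 20) the treated part. Assume that the degree is even across patches and that untreated skin does not change.

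- Largest possible T-VASI improvement = min(B, 20)/B.
- Repigmentation of treated skin needed for T-VASI50 = 0.5B/min(B, 20).

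| B (% BSA) | Largest possible improvement | Needed in treated skin |
|---|---|---|
| up to 20 | 100% | 50% |
| 25 | 80% | 62.5% |
| 30 | 66.7% | 75% |
| 35 | 57.1% | 87.5% |
| 40 | 50% | 100% |
| 50 | 40% | 125% (not possible) |

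**3. How firm is the 40% point?** It depends on both assumptions.

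- *Uneven degree.* With degree dt in treated and du in untreated patches, the cut-off is 20 + 20 × dt/du. For 0.75 vs 1 it is 35%; for 1 vs 0.75, 46.7%; for 1 vs 0.5, 60%. Sharper contrasts move it further: 30% for 0.5 vs 1, and 100% (in effect no limit) for 1 vs 0.25.
- *Untreated skin changes.* If it improves by a fraction u, response needs (20 + (B − 20)u)/B of at least 0.5, so the cut-off is 20(1 − u)/(0.5 − u). For 10% worsening it is 20 × 1.1/0.6 = 36.7%; for 10% improvement, 20 × 0.9/0.4 = 45%; for 20% improvement, 20 × 0.8/0.3 = 53.3%.

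The weaker statement, that response is harder above 20%, needs only that untreated skin improves less than treated skin.

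**4. Illustrative effect on T13.** The response rates and the blocked share q are assumptions; neither is in the documents. Both rates are multiplied by (1 − q). Power is exact Fisher with 30 per arm and two-sided alpha 0.0125, the first Holm step of 0.025.

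| Rates in subjects able to respond | q = 0 | q = 5% | q = 10% | q = 20% |
|---|---|---|---|---|
| 50% vs 15% | 57% | 53% | 48% | 40% |
| 50% vs 20% | 37% | 33% | 30% | 24% |

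For 50% vs 20% the difference shrinks from 30 points to 30 × 0.9 = 27 and 30 × 0.8 = 24.

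**5. Chance imbalance.** Randomization is stratified by age only. If 20% of subjects exceed 20% BSA (assumed), two arms of 30 differ by 4 or more such subjects with probability 26%; if 10% do, 13%.

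**The case against.** **Extent is not ignored everywhere.** Baseline total BSA is tabulated, so an imbalance would be seen. T-VASI percentage change, which has no 50% threshold, is summarized by treatment and visit (SAP 7.4.2). PaGIC-V asks about treated areas. Parts of the SAP around 7.5 and after 7.6 are blacked out, so a hidden supportive analysis cannot be excluded. This stands, and it confines the point to the visible T13/T23 model.

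**The size is unknown and T13 is weak anyway.** With nobody blocked, power is 57% or 37% on the assumed rates. At 5% blocked the loss is about 4 points. The tests are reached only after the primary tests and T12 and T22 succeed. All of this stands.

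**The remedy is partial.** The power figures concern subjects who cannot respond, whereas the proposed split is at 20%. That split pools a subject at 21% BSA, who needs 0.5 × 21/20 = 52.5%, with subjects who cannot respond at all. Dropping blocked subjects outright, with equal arms of 27 or 24, lifts power only from 48% to 51% or from 40% to 44%. Still, the gain is not nil: simulation of the 20% split on assumed rates (30 per arm, alpha 0.0125) gave 1 to 9 points more power, also with exact conditional tests.

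**A reader might infer that chance imbalance could pass for a dose effect and make the tests invalid.** The documents do not support that. Allocation is randomized, and the type I error rate already allows for chance imbalance. Adjustment here improves precision and interpretation; it does not correct a bias.

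**Conclusion.** The concern holds in a limited form. The cap, the absence of an upper entry limit and the whole-body score together make T-VASI50 harder to reach above 20% BSA, and the visible Week 52 model leaves out the baseline variable that carries this. The consequence is a diluted dose contrast and lost precision in T13 and T23, with no inflation of type I error.

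A reader might conclude that response is impossible for everyone above 40% BSA. The documents do not establish that. The figure rests on even depigmentation and unchanged untreated skin, while degree is scored per body site in seven coarse steps, and Protocol 1.1 mentions some spontaneous repigmentation in 10% to 20% of patients. A cut-off of roughly 35% to 60% covers moderate departures.

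Nor do the documents show how many subjects lie above 20% or 40%. If few do, the effect is small. The power losses (57% to 48% or 40%; 37% to 30% or 24%) are illustrations on assumed rates. Whole-body T-VASI50 is a legitimate endpoint, and nothing here calls for changing it or the treatment rule.

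**What to change.** Keep whole-body T-VASI50 as the key secondary endpoint and leave the treatment rule as it is. In the SAP:

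- add baseline affected BSA (at most 20% vs above 20%) to the Week 52 T-VASI50 logistic model in 7.4.1, with the exact method already planned in 7.3.1 if cells are sparse;
- add a supportive T-VASI50 analysis in subjects at or below 20% BSA at baseline;
- report the numbers above 20% and above 40% BSA by arm.

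The data are already collected. The cost is SAP wording, one extra table and one more model term with about 30 subjects per arm, which adds some sparse-data risk. The supportive analysis adds no confirmatory power; it helps the reader interpret T13 and T23.
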